LSMD	Least Squares Mean Difference
PD	Pharmacodynamic
PGIS	Patient Global Impression of Severity
PK	Pharmacokinetics
PT	Preferred Term
SAE	Serious adverse event
SAP	Statistical Analysis Plan
SoA	Schedule of Activities
SoC	Standard of Care
SOC	System Organ Class

AMENDMENT HISTORY

CATEGORY Change refers to:	Date	Description of change	In line with CSP?	Rationale
N/A	5/13/2024	Initial approved SAP	See section 2	N/A
See description	12/12/2024	Updated Changes to protocol.	See section 2	Previous changes vs CSP were implemented into CSP. The added change is due to no CCI [REDACTED] for Japan and very few subjects in one of the CCI [REDACTED] [REDACTED] for rest of the world.
See description	12/12/2024	Added clarification that PKS will be analysed using assigned treatment group.	See section 2	Clarification
See description	12/12/2024	Added rules for number of decimals.	See section 2	Clarification
See description	12/12/2024	Updates to baseline definitions.	See section 2	Minor corrections to the definitions.
See description	12/12/2024	Added clarifications to imputations rules for dates. Adjusted definitions of prior and concomitant medication to align with current AZ standard.	See section 2	Align with data collection and standard definitions.
See description	12/12/2024	Added visit windowing for variables that are collected daily and that are composite endpoints.	See section 2	Due to nature of variables needed to add additional visit windowing.
See description	12/12/2024	Added Japanese specific analyses.	See section 2	Scope of TLFs was extended.
See description	12/12/2024	Added cirrhosis etiology characteristics.	See section 2	Missed in previous version.

See description	12/12/2024	Added clarification about dose interruptions for compliance.	See section 2	Clarification
See description	12/12/2024	Updated analyses method and population summary for exploratory objectives.	See section 2	Correction of previous and aligning with analyses used for key objectives.
See description	12/12/2024	Added clarification about how to handle values below lower limit of detection.	See section 2	Clarification
See description	12/12/2024	Added CCI for composite endpoints.	See section 2	Requested by FDA.
See description	12/12/2024	Added seed and information about number of imputations.	See section 2	Was missed to be specified in first version.
See description	12/12/2024	Added information about how to derive and analyse PRO.	See section 2	More detailed information added
See description	12/12/2024	Added information about additional AE outputs.	See section 2	Clarification and extended TLF scope.
See description	12/12/2024	Corrections and clarifications added to laboratory safety section. Information about additional KSI and individual graphs of laboratory data added.	See section 2	Clarification and extended TLF scope.
See description	12/12/2024	Clarifications to ECG section added.	See section 2	Clarification

1 INTRODUCTION

The purpose of this document is to give details for statistical analysis of study D4326C00004 supporting the clinical study report. The reader is referred to the CSP and the CRF for details of study conduct and data collection.

2 CHANGES TO PROTOCOL PLANNED ANALYSES

Note that this section lists deviations as from current CSP at the time of signing this SAP version. Future CSP amendments might include below listed topics and if so the SAP will no longer deviate from the CSP.

CSP states that the analysis model will include the fixed categorical effects of CCI [REDACTED] factor but this will not be included in the models. Reason for change is that there is no CCI [REDACTED] for Japan and very few subjects in one of the CCI [REDACTED] for rest of the world.

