4 STUDY DESIGN

4.1 Overall Design

This is a Phase IIb multicentre, randomised, double-blind, parallel-group, placebo-controlled study to evaluate the safety of zibotentan/dapagliflozin in combination as compared to zibotentan monotherapy as well as zibotentan/dapagliflozin and zibotentan monotherapy as compared to placebo in patients with cirrhosis. Eligible participants should have a history of decompensation events or compensated cirrhosis with signs of CSPH. If compensated cirrhosis, the eligible participant must have signs and measures that would indicate that the participant has CSPH and includes, but not limited to, presence of gastro-oesophageal varices at endoscopy or collaterals at imaging (either one within 12 months prior to screening), and/or **CCI** [redacted] kPa, or of **CCI** [redacted] kPa with **CCI** [redacted] (at time of screening). Participants should have a MELD score < 15 and should be classified as Child-Pugh A or B ([Table 6](#)).

It is planned that approximately 22 eligible participants will be randomised to each of the 3 treatment groups, for a total of up to 66 participants (see [Figure 1](#)). For details of the study assessments, please see SoA ([Table 1](#)).

This study will consist of the following periods:

Screening Period of up to 3 weeks: The Screening Visit (Visit 1) will take place between 7 to 21 days before the Randomisation Visit (Visit 2) to confirm participant eligibility and collect baseline data. There must be at least 7 days between Visit 1 and Visit 2 to allow sufficient time for laboratory results to be examined. At the Randomisation Visit (Visit 2), eligibility criteria will be reassessed, safety laboratory data reverified, and participants will be provided digital devices to measure their body weight starting the first day after the Randomisation Visit and every day at home.

Treatment Period of 6 weeks: During the Treatment Period, participants will visit the study centre 5 times. At Visit 2, participants will be randomised and will receive the first dose of the study intervention. At each study visit during the treatment period (from Visit 2 till Visit 6) participants will receive the once daily dose at the study centre and will provide a pre-dose blood sample for PK analysis and other lab samples before the intake of study intervention. When not visiting the study centre the patients will take the once daily dose of study intervention at home.

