6.3 Assignment to Study Intervention

All participants will be centrally assigned to randomised, blinded study intervention using an IRT/RTSM. Before the study is initiated, directions for log in will be provided to each study centre. The IRT/RTSM will provide to the investigators or pharmacists the kit identification number to be allocated to the participant at the dosing visit. Routines for this will be described in the IRT/RTSM user manual that will be provided to each study centre.

A separate randomisation list will be provided for Japan sites.

In this study, eligible participants will be randomised to Treatment Groups 1 to 3 with equal allocation (1:1:1). Japan will have up to 5 participants per arm (out of 22).

Participants will be **CCI** to the **CCI** of **CCI** at the time of randomisation, to ensure an approximate balance between treatment groups within each sub-population. There will be no **CCI** for Japanese participants as it may lead to **CCI** for the study.

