9.2 Sample Size Determination

Approximately 22 participants are planned to be randomised to each of the 3 treatment groups. The sample size is not determined based on a formal statistical hypothesis testing for this Phase IIb study. With **CCI** evaluable participants per treatment group, an observed difference of **cc**% (**CCI**%) in proportion of participants with the composite of fluid retention between 2 treatment groups and an observed **cc**% composite of fluid retention in the corresponding zibotentan group, the lower limit of a two-sided 90% CI for the difference will be **cc**%.

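### SAP section 2 drops what appears to be the randomisation factor and announces no replacement term for the separate Japan list, so the model-based 90% CIs may be somewhat too wide

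*SAP*

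**What the plan says.** Protocol 6.3 restricts allocation in two ways. Participants are subject to a feature, its name blacked out, that is applied "at the time of randomisation, to ensure an approximate balance between treatment groups within each sub-population". Japan is handled apart: "A separate randomisation list will be provided for Japan sites", without that feature. Allocation is equal across the three arms, and Japan may supply at most 5 of the 22 participants in each.

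SAP section 2 lists departures from the protocol's analyses. It says that the protocol's model contains a categorical factor (name blacked out), "factor but this will not be included in the models". The reason given is that there is no such feature "for Japan and very few subjects in one of the" rest-of-world groupings. The section names no term that takes its place.

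The models concerned are the MMRMs for the continuous key endpoints (SAP 4.2.2.4, 4.2.3.4 and 4.2.5.4), whose terms are redacted. The ANCOVA sensitivity analyses in 4.2.2.5, 4.2.3.5 and 4.2.5.5 vary the method or the handling of missing data, not this choice. Reported intervals are generally two-sided 90% (SAP 3.3).

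**The concern.** When arms are balanced within lists or levels, differences between those groups largely cancel out of the treatment contrast. A model without the grouping leaves the same differences in the residual. The standard error then describes a less tightly controlled allocation than the one used, and the interval is too wide if the grouping predicts the outcome.

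Neither stated reason prevents an additive term. A factor that is undefined for Japan can be given a Japan level, and a sparse level can be pooled.

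Japan could plausibly matter. SAP Table 2 counts 20 mg of torsemide as one loop-diuretic equivalent globally but 8 mg in Japan, so the diuretic endpoint is scaled differently there. That makes a difference plausible; it does not show its size.

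The trial makes no formal hypothesis tests, so for the continuous key endpoints the estimates and their 90% CIs are the result. With 22 per arm, avoidable width makes an effect on weight, water or blood pressure harder to see.

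**Working it through.** **Inputs from the documents.** The design has 22 "randomised to each of the 3 treatment groups, for a total of up to 66 participants", and 3 × 22 = 66 agrees. Japan is at most 3 × 5 = 15 of 66 (22.7%). Intervals are two-sided 90%. Protocol 9.2 says "The sample size is not determined based on a formal statistical hypothesis testing for this Phase IIb study", and the inputs and result of its precision statement are redacted, so there is no planned width to reproduce.

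**Assumptions.** The documents do not give the prognostic strength of the factor or of Japan, or the size of the sparse level. The check assumes shifts of 0, 0.5 and 1 residual SD, and a sparse level of 3, 6 or 10 patients.

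**Formula for one omitted grouping.** With a share p of patients, a shift of d residual SDs and balance across arms, the SE without the term divided by the SE with it is √(1 + p(1−p)d²).

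| Group size | p(1−p) | d = 0.5 | d = 1 |
|---|---|---|---|
| 15 of 66 (Japan at its cap) | 0.1756 | √1.0439 = 1.022 | √1.1756 = 1.084 |
| 10 of 66 | 0.1286 | √1.0321 = 1.016 | √1.1286 = 1.062 |
| 6 of 66 | 0.0826 | √1.0207 = 1.010 | √1.0826 = 1.040 |
| 3 of 66 | 0.0434 | √1.0108 = 1.005 | √1.0434 = 1.021 |

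In participants, Japan at its cap is worth 66 × 0.0439/1.0439 = 2.8 of 66 at 0.5 SD and 66 × 0.1756/1.1756 = 9.9 of 66 at 1 SD. The same rows apply to a smaller Japan share: 6 Japanese participants would give about 1% or 4%.

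**Simulation.** A single-visit ANCOVA with a baseline covariate stood in for the MMRM. Each scenario had 66 patients (15 from Japan), three arms, permuted blocks of 3 within each list or level, and 6,000 runs. Ranges run over the three sparse-level sizes.

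| Assumed shift | CI width without terms ÷ with | Coverage without terms |
|---|---|---|
| None | 0.999–1.000 | 89.8–90.2% |
| Sparse level only, 0.5 SD | 1.005–1.015 | 89.7–90.9% |
| Sparse level only, 1 SD | 1.021–1.064 | 90.6–91.9% |
| Japan only, 0.5 SD | 1.022–1.023 | 90.2–90.8% |
| Both, 0.5 SD | 1.024–1.029 | 90.6–91.0% |
| Both, 1 SD, same direction | 1.099–1.116 | 92.4–92.8% |
| Both, 1 SD, opposite directions | 1.118–1.179 | 93.5–94.3% |

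Coverage with the terms was 89.6–90.6% throughout. The Monte Carlo standard error is √(0.9 × 0.1/6000) = 0.4 percentage points, so 89.7% is not evidence of under-coverage.

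A separate simulation with 5 Japanese participants per arm and Japan alone at 1 SD gave half-widths of 0.547 and 0.503, a ratio of 1.087, and 92.4% coverage without the term. This agrees with 1.084 from the formula.

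**The case against.** The best defence is that the change is declared, with its reasons, in SAP section 2 and in the amendment history. Leaving a factor with a nearly empty level out of a 66-patient repeated-measures model is a defensible choice. There are no tests, so type I error is not at issue, and any error makes the intervals cautious. All of this stands, and it keeps the point to one of precision.

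Three stronger readings are tempting, and the documents do not support them.

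- **The intervals are wider.** A reader might take this as established. It holds only if the factor or Japan predicts change beyond the other model terms, and nothing in either document gives that strength. With no effect the width ratio is 0.999–1.000.
- **The SAP ignores the Japan list.** A reader might infer this from the lack of a visible term. The model terms are redacted, so absence cannot be confirmed, and section 2 cites Japan as a reason for the change. What can be said is that no replacement is announced or visible.
- **The main fluid-retention results are affected.** They are not. Key objectives 1, 2, 7 and 8 use Clopper-Pearson and Chan-Zhang intervals (SAP 4.2.1.4 and 4.2.4.4), which carry no model terms.

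The defence does not show that the factor had to go. Sparsity justifies pooling the rest-of-world levels. It does not justify leaving out Japan versus the rest of the world, which may be the larger group.

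**Conclusion.** The point holds as a modest, conditional loss of precision in the continuous key endpoints. Omitting the terms widens the 90% CIs by about 0.5% to 3% at a 0.5 SD shift in one or both groupings, and by about 2% to 8% for one grouping at 1 SD. Only strong effects of both, at 1 SD each, bring it to 10% to 18%, and nothing in the documents supports effects of that size. If neither grouping predicts the outcome, nothing is lost.

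The error is conservative: coverage without the terms ran from about 90% up to 94.3%. It does not make the analysis invalid.

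The conclusion rests on four things. The blacked-out factor is taken to be the randomisation factor, a fair inference because Protocol 6.3 and SAP section 2 describe the same exception for Japan. Japan is set at its cap of 15 of 66. The shifts and the sparse-level sizes are assumed. A single-visit model stands in for the MMRM.

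**What to change.** In SAP 4.2.2.4, 4.2.3.4 and 4.2.5.4, and in the matching ANCOVA sensitivity analyses, add one categorical main effect for randomisation group. Its levels are the Japan list and each rest-of-world level. Prespecify a rule, applied to blinded data, that pools the rest-of-world levels and keeps Japan versus rest of world if a level is too sparse. State the minimum count that triggers it.

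Rewrite the deviation in section 2 to say that this term replaces the protocol's factor. Do not delete it: that factor has no Japan level, so the new term still differs from the protocol and must be declared.

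The cost is SAP wording, one model term and 1 to 2 degrees of freedom: 1 for Japan versus rest of world, or 2 if there are two rest-of-world levels. In the single-visit stand-in, with 66 − 4 = 62 residual degrees of freedom, that leaves 60 or 61.

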3 DATA ANALYSIS CONSIDERATIONS

3.1 Timing of Analyses

This study will have no interim analysis but there are originally two planned DMC meetings during the study to monitor safety as specified in the DMC Charter. At the time of SAP amendment it was known that the study would only have one DMC meeting before last subject last visit. The DMC works independent of the Global Study Team and will review unblinded study safety data.

The final clinical data lock for writing the CSR will occur once all subjects have completed their full study participation or withdrawn from study.

3.2 Analysis Populations

The following analysis sets are defined for the study and detailed in [Table 1](#):

Table 1 **Populations for Analysis**

Population/analysis set	Description
Screened analysis set	All participants who signed the ICF. Unless otherwise stated, the enrolled set will be used for the presentation of disposition data.

Population/analysis set	Description
FAS	All participants who are randomised and receive any study intervention. Participants are evaluated according to the treatment assigned at randomisation. The FAS will be the analysis set for all endpoint analyses with the exception of the PK analyses.
PKS	All participants in the FAS who have at least one detectable zibotentan or dapagliflozin plasma concentration measurement post-treatment. Participants are evaluated according to the treatment assigned at randomisation. Pharmacokinetic samples collected after Visit 5 may be excluded from the PKS and may be reported outside the CSR. The PKS will be used for all PK analyses.

Abbreviations: FAS: Full Analysis Set; ICF: Informed consent form; PKS: Pharmacokinetic Analysis Set; PK: Pharmacokinetics.

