8.5.2 Determination of Drug Concentration

Samples for determination of drug concentration in plasma will be assayed by bioanalytical test sites operated by LabCorp on behalf of AstraZeneca, using an appropriately validated bioanalytical method. Full details of the analytical method used will be described in a separate Bioanalytical Report.

Drug concentration information that would unblind the study will not be reported to investigative study centres or blinded personnel until the study has been unblinded. Only samples from participants on active treatment will be analysed, unless there is a need to confirm that correct treatment has been given to study participants.

Incurred sample reproducibility analysis, if any, will be performed alongside the bioanalysis of the test samples. The results from the evaluation, if performed, may be reported in a separate Bioanalytical Report.

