9.4.3 Safety

Safety analyses will be performed using the FAS. Safety data will be presented using descriptive statistics unless otherwise specified. In general, the baseline value for statistical analysis is the last nonmissing value prior to administration of the first dose of study intervention. Details will be described in the SAP.

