3.3 General Considerations

The FAS will be used for all analyses unless otherwise stated.

Descriptive summaries of continuous data will be done by following statistics, unless otherwise stated, n, mean, SD, minimum, median, and maximum as appropriate. Q1 and Q3 may also be shown.

Descriptive summaries of categorical data will be done as the number and percentage of subjects in each category for each treatment group. When appropriate, for study population the number of missing observations will be presented, and these will be included in the denominator when calculating percentages unless otherwise stated. For treatment emergent and shift tables number of observations will be used as denominator. For AE tables the denominator will be the number of participants within the analysis set.

In general the reported CIs will be 90% two-sided intervals.

A general rule is to present descriptive summary statistics (mean, SD, median, Q1, Q3, Confidence intervals (CI) and standard error (SE)) to 1 more decimal place than the individual values. The minimum and maximum values should be reported to the same number of decimal places as the individual values. In general, the maximum number of decimal places reported shall be three for any summary statistics. Categorical data presented as percentages will be presented to one decimal place.

When coding using MedDRA the most recent version of the MedDRA that have been released for execution at AstraZeneca or designee will be used.

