4.2.6.4 Primary Analysis of exploratory objective

The data will be descriptively summarised by treatment group, visit, and time-point. Geometric mean and CV will be presented in addition to arithmetic mean and SD. PK assessments that should only be collected once according to schedule of activities in CSP will be summarised using the assessment closest to target date even if outside of visit windowing.

Additional PK analyses may be conducted as appropriate but will be reported outside the CSR.

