4.6.2.2 Presentation

The number and percentage of subjects with AEs will be tabulated by treatment group. For subject count presentations, subjects will only be counted once per category, regardless of the number of AEs satisfying the condition.

The following summaries will be presented:

Overall summary of AEs

Number of subjects with any AE, any SAE, any AE with outcome of death, any AE leading to discontinuation of IP, any AE leading to interruption of IP, any AE possible related to IP and any AESIs (see section 4.6.8) will be presented. This will also be presented for Japanese sub-population.

By SOC and PT

Separate AE tables by SOC and PT will be provided for: Any AE, any SAE, any AE with outcome of death, any AE leading to discontinuation of IP, any AE leading to interruption of IP and any AE possible related to IP. AE table by SOC and PT for any AE will also be presented for Japanese sub-population. Event count table will be presented for AEs and SAEs by SOC and PT.

By PT

Separate AE table sorted by decreasing frequency on PT level will be presented.

Maximum intensity

AEs will be presented by their maximum intensity for all AE and by PT.

Most common non-serious AEs

A table of non-serious AEs occurring in more than 5% of subjects in any treatment group will be presented by SOC and PT.

Assessment of potential proarrhythmic effect

A table with number and percentage of subjects with PTs relevant for assessment of potential proarrhythmic effect will be presented. PTs are based on the SMQ Torsade de pointes/QT prolongation (narrow and broad scope).

Key subject information

Key subject information for subjects with SAEs, AEs with outcome death and AEs leading to discontinuation of IP will be provided.

Key subject information will also be presented for subjects with modified Hy's law during the study, if appropriate a summary table will be produced.

Listings and narratives

An AE listing including individuals in FAS covering details for each individual AE will be produced. An AE listing for participants who were randomized but not exposed to study intervention is presented separately. SAEs occurring prior to start of study intervention will be included in data listings. Narratives may also be produced.

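### Safety and PK summaries are grouped only by assigned treatment, so a kit error, if one occurred, would report a participant's results under an arm whose drug they did not take

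*SAP*

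**What the plan says.** SAP 3.2 (Table 1) uses one grouping rule for both the FAS and the PKS: "Participants are evaluated according to the treatment assigned at randomisation". Protocol 9.3 (Table 8) has the same rule for the FAS but gives none for the PKS. The SAP amendment history shows that the PKS rule came in with the December 2024 amendment: "Added clarification that PKS will be analysed using assigned treatment group".

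The sets are then applied as follows.

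- **Safety.** Protocol 9.4.3: "Safety analyses will be performed using the FAS". SAP 3.3: "The FAS will be used for all analyses unless otherwise stated". SAP Table 8 also names the FAS for the safety objective. For AEs, SAP 4.6.2.2 says "The number and percentage of subjects with AEs will be tabulated by treatment group".
- **PK.** SAP 3.2: "The PKS will be used for all PK analyses". SAP 4.2.6.4: "The data will be descriptively summarised by treatment group, visit, and time-point".
- **Deviations.** SAP 3.3.5 lists investigational product deviations as an important category and says that deviations do not remove anyone from the analyses.

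Neither document defines an as-treated set, an actual-treatment variable or a sensitivity table by treatment received.

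**The concern.** The trial is a safety study. Protocol 8.2 says it has no efficacy assessments, and protocol 4.2 says the purpose is to compare zibotentan with and without dapagliflozin, with placebo as reference. AEs, laboratory values, ECGs, vital signs and plasma concentrations follow from what a participant took. If someone took another arm's kit, grouping by assignment attributes those results to the wrong drug. In expectation this draws the arms together, which is the unfavourable direction when the question is harm.

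Entry to the PKS depends on exposure (at least one detectable concentration), but grouping within it depends on assignment. The protocol also foresees checking what was actually taken: section 8.5.2 restricts assays to participants on active treatment "unless there is a need to confirm that correct treatment has been given to study participants". The SAP has no rule for using the answer in the tables.

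**Working it through.** **No figure in the plan to reproduce.** The rates, evaluable number and confidence limit in the sample-size statement are redacted. Only the total can be checked: 3 × 22 = 66, as stated. The event counts below are assumptions.

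**Step 1: what happens to a mis-dosed participant under the text.**

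| Assigned | Taken | Safety tables | PK tables |
|---|---|---|---|
| Monotherapy | Combination | Under monotherapy | Dapagliflozin concentrations under monotherapy |
| Combination | Monotherapy | Under combination | Zibotentan without dapagliflozin, under combination |
| Placebo | Zibotentan | Under placebo | Ordinarily not assayed; in the PKS, under placebo, only if assayed to confirm treatment |
| Active | Placebo only | Under the active arm | Nothing detectable, so not in the PKS |

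The third row follows from protocol 8.5.2 together with protocol 6.4, under which the staff analysing PK samples hold the randomisation code.

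**Step 2: weight of one participant.** With 22 per arm (protocol 9.2), 1/22 = 4.5 percentage points.

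**Step 3: shift in a risk difference.** Let p and z be the event counts by assigned arm on placebo and zibotentan. Suppose one of the p events belongs to a placebo-assigned participant who took zibotentan. Regrouping gives arms of 21 and 23, and the risk difference (zibotentan minus placebo) changes by

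[(z + 1)/23 − (p − 1)/21] − [z/22 − p/22] = (22 − z)/506 + (22 − p)/462.

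| p | z | By assigned arm | By treatment received | Shift (points) |
|---|---|---|---|---|
| 2 | 8 | 27.3% | 34.4% | 7.1 |
| 3 | 9 | 27.3% | 34.0% | 6.7 |
| 4 | 8 | 18.2% | 24.8% | 6.7 |

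The expression falls as p or z rises. Since p is at least 1, its maximum is at p = 1, z = 0: 22/506 + 21/462 = 4.35 + 4.55 = 8.9 points.

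Two such participants, under the same assumed counts, shift the difference by 13.5 to 14.4 points.

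**Step 4: a rare event.** If the mis-dosed participant has the only event among those assigned placebo, placebo reads 1/22 = 4.5% by assigned arm (Clopper-Pearson 90% CI 0.2 to 19.8). By treatment received it reads 0/21 = 0% (90% CI 0 to 13.3).

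**Step 5: the direction is not guaranteed.** If the mis-dosed participant has no event, p = 3 and z = 9 give 9/23 − 3/21 = 24.8 points by treatment received, against 27.3 by assigned arm. Regrouping then narrows the contrast.

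**Step 6: which trace of an error remains.** Important deviations are tabulated by category and listed by participant (SAP 4.1.3.2). AEs are listed individually (SAP 4.6.2.2). Wrong-drug events are reportable within 24 hours (protocol 8.4.10), but protocol Appendix B 4 exempts errors arising from the IRT/RTSM. None of this alters an AE, laboratory, ECG or PK table.

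**The case against.** The strongest reply is that this is a stated, coherent choice. Protocol and SAP agree on the FAS rule, SAP 4.6 adopts a treatment policy strategy for safety, and the FAS already requires at least one dose, so no dosed participant is left out. Only the grouping label is at issue. Kits are allocated by number through the IRT/RTSM (protocol 6.3), and a second staff member confirms doses given at the site (protocol 6.5).

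Most of that stands. But the treatment policy wording gives premature discontinuation and prohibited medication as its examples; receipt of another arm's kit is not addressed. The second-person check does not cover doses taken at home, and capsules and tablets come in separate bottles (protocol Table 4), so one component alone can go wrong.

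Four stronger readings are tempting, and the documents do not support them.

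- **That a placebo participant who took zibotentan would enter the PKS as a matter of course.** Under protocol 8.5.2 the samples would ordinarily not be assayed. Entry needs the confirmation exception, and then an error is already suspected.
- **That harm would be hidden.** With about 66 participants and individual listings of deviations and AEs, a mix-up that was recorded could be traced. The summaries would misattribute it; the listings would not.
- **That a shift of about 9 points is typical.** It needs one placebo event and no zibotentan events by assigned arm.
- **That the main fluid-retention result should also be regrouped.** Fluid retention AEs are a component of the key composite. Grouping that composite by assigned arm fits its estimand, so that component would not move under the fix.

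**Conclusion.** The point holds as a minor, conditional weakness. All safety summaries, and under the SAP all PK summaries, are grouped by assigned treatment, and nothing is planned by treatment received. After a kit error, exposure-driven results would be reported under the wrong drug. For PK the clear case is a swap between monotherapy and the combination.

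The size is 4.5 points of an arm per participant. One participant with an event moved from placebo to zibotentan shifts a risk difference by about 7 points, with a ceiling of 8.9. This rests on 22 analysed per arm, one mis-dosed participant who has an event, and assumed counts of 2 to 4 placebo and 8 to 9 zibotentan events. The documents report no dispensing error, and if none occurs every table is unchanged.

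**What to change.** Keep the key endpoints, including the fluid-retention composite, by assigned treatment. In SAP 3.2 and protocol Table 8, state that the safety summaries in SAP 4.6 and the PK summaries in SAP 4.2.6 are by treatment actually received.

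Set the classification rule before unblinding and define it for zibotentan and dapagliflozin separately, for example by the treatment taken for most of the dosing period. A simpler rule, under which any zibotentan dose counts as zibotentan, is not enough. It cannot place a participant who took dapagliflozin alone, for which there is no arm. It does not say where monotherapy with added dapagliflozin belongs, and it would reclassify someone after a single wrong dose. Exposures that match no arm, and brief wrong exposure, should be footnoted and listed.

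The cost is a small derivation of an actual-treatment variable and matching text in both documents. If an error occurs, safety denominators may differ slightly from those of the key endpoints. Body weight and supine blood pressure, which appear both as key endpoints and as vital signs, would then be grouped in two ways, and the tables should say so. If no error occurs, nothing changes.
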